#### *b. Secondary Outcomes*

The proportion of rescue narcotics will be compared between the ketorolac and placebo groups. Narcotics will be converted to standard morphine equivalents for statistical comparison.

On day two, the research fellow will also ask patient's his/her Global Evaluation of Study Medication by telephone. The patient will be asked, "How would you rate the study medication you received to delay pain". The choices will be on a four point scale: 1=poor; 2=fair; 3=good; 4=excellent.

Adverse events will be obtained from a standard form included in the patient's study diary. The proportion of adverse events will be compared between the ketorolac and placebo groups.

Time to regular shoe gear will be compared between the two groups. This information will be assessed during the post-operative visits and recorded within the secure BIDMC online medical record for each patient. Level of post-operative activity will also be evaluated with the help of the functional recovery index. This is a validated instrument for post-operative patients which includes three main domains: 1. Pain and social activity; 2. Lower limb activity; 3. General physical activity.

Summary statistics will be analyzed and reported. Continuous data will be analyzed with a 2-sided student's t-test if normally distributed or a Wilcoxon Rank Sum test if it cannot be justified through the Central Limit Theorem. From this data, confidence limits will be obtained and a 2-sided p value of  $\leq 0.05$  from the Fisher Exact Test will be considered statistically significant. If there are significant confounders identified, multivariate regression or stratification may be required and utilized if necessary. Binary data points will be compared by chi square analysis. From this, 95% confidence intervals will be obtained as well as a p-value from the Fisher Exact Test. A compliers-only analysis will also be secondarily performed if necessary, with the notion that this part of the study may have confounders and will not be part of the randomized comparison. Table 1 of the study will detail subject ages, gender, comorbidities, and other baseline study demographics.

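### The continuous secondary outcomes are assigned a t-test or Wilcoxon test, but the sentence that decides significance takes the p-value from Fisher's exact test

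*Combined protocol and SAP*

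**What the plan says.** The rule is in the closing paragraph of the Secondary Outcomes section, under Data Analysis in the Statistical Considerations. It runs in this order:

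1. The test for continuous data: "Continuous data will be analyzed with a 2-sided student's t-test if normally distributed or a Wilcoxon Rank Sum test", the latter where normality cannot be relied on.
2. The next sentence, on the same data: "From this data, confidence limits will be obtained and a 2-sided p value of" at most 0.05 "from the Fisher Exact Test will be considered statistically significant".
3. A sentence on adjustment for confounders.
4. The test for binary data: "Binary data points will be compared by chi square analysis".
5. The sentence after it: "95% confidence intervals will be obtained as well as a p-value from the Fisher Exact Test".

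Outcomes in the same section that fall under the continuous rule include opioid use ("Narcotics will be converted to standard morphine equivalents for statistical comparison") and activity ("Level of post-operative activity will also be evaluated with the help of the functional recovery index"). Time to regular shoe gear belongs with them if it is handled as a continuous variable.

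**The concern.** Fisher's exact test is a test on a contingency table. It has no version that returns the p-value for a difference in means or for a rank comparison. Taken word for word, the sentence asks for a quantity that the named analysis does not produce.

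Two things follow for the outcomes concerned. First, the written significance criterion cannot be applied to the test that the plan names, so an analyst has to set part of the text aside. Secondly, the confidence limits would come from the t-test or Wilcoxon analysis while the significance call came from elsewhere, so the two could disagree. A rule that needs interpretation is best settled before the data are unblinded, so that nobody can later ask which test was chosen and when.

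**Working it through.** **Which data does the first Fisher mention govern?** The sentence refers back to the data of the sentence before it, which is about continuous outcomes. Binary outcomes are introduced only two sentences later and carry their own statement that the p-value comes from Fisher's test. The first mention therefore cannot be the binary rule placed early. It attaches to the continuous outcomes.

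**Does anything in the plan make Fisher usable there?** It would need a cut-point or a set of categories. The section gives none for morphine equivalents, the functional recovery index or time to shoe gear.

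**Does the error reach the main outcomes?** No. The Primary Outcome section analyzes pain at 48 hours by regression, with its own threshold of 0.05. It analyzes delayed union and nonunion by logistic regression, again with a two-sided threshold of 0.05.

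**Is there a plan figure to reproduce?** No. The Sample Size Justification covers only VAS pain and delayed or nonunion, so no secondary outcome has a stated power.

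**Hypothetical illustration.** This shows only why the choice of test is not cosmetic. It describes an analysis that the plan does not propose.

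Inputs:
- 40 per arm, from the Sample Size Justification (80 subjects before the allowance for drop-outs).
- Two-sided alpha of 0.05, from the plan.
- Assumed: normal data with equal variances, a difference that the t-test detects with 80% power, and a cut fixed in advance at the pooled population median.

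Steps:
1. Solve for the standardized difference d that gives the two-sample t-test power 0.80, with 2 × 40 − 2 = 78 degrees of freedom and noncentrality d × √(40/2). The result is d = 0.634.
2. The pooled median lies d/2 = 0.317 from each mean. The proportions above the cut are Φ(0.317) = 0.624 and 1 − 0.624 = 0.376.
3. Exact power of Fisher's test = Σ Bin(i; 40, 0.624) × Bin(j; 40, 0.376), summed over all pairs (i, j) whose two-sided Fisher p-value is at most 0.05. The result is 0.546.
4. The difference is 0.80 − 0.546 = 0.254, about 25 percentage points. With the same split, 70 per arm would be needed to return to 80% (0.805).

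For comparison, simulation under the same assumptions gives the Wilcoxon test about 77% power, so either test named in the plan does far better than the split.

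**The case against.** The strongest reply is that this is a slip that no competent analyst would follow. The plan also states, as a rule in its own right, that continuous data are analyzed by t-test or Wilcoxon test. Each of those tests yields a two-sided p-value, and the threshold of 0.05 is clear and the same as for the other outcomes. Only the attribution to Fisher is out of place. On this view the natural reading is already correct.

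Most of that stands, and it limits what may be concluded. It does not make the sentence right: the plan's explicit significance statement for these outcomes still names a test that cannot apply.

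Three stronger readings are tempting, and the documents support none of them.

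- A reader might infer that the analyst will be forced to dichotomize, or to tabulate every distinct value, and so lose power. The plan gives no cut-point, split or table of that kind, and a valid test is already named. The 55% figure shows what dichotomizing costs under assumed data. It is not an expected loss in this trial.
- A reader might infer that the trial's main conclusions are exposed. They rest on the regression analyses and do not use this sentence.
- A reader might infer that the opioid outcome is also wrongly defined, because the section says "The proportion of rescue narcotics will be compared between the ketorolac and placebo groups", and might want it fixed as use from 0 to 48 hours. The wording is loose, but the sentence on morphine equivalents, and the common scale mentioned under Patient Standard of Care, point to an amount. No section sets a 48-hour window for opioid use. Consumption is obtained again at week one, and study drug runs for five days, so a longer window fits the documents equally well. The week-one record is gathered by pill count and may not give reliable clock times. Choosing a window would be a preference and is not part of this point.

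**Conclusion.** The point holds as an internal inconsistency in wording. The stated significance rule for continuous secondary outcomes names a test that does not apply to them, most likely because text from the binary-data sentence was repeated. Its reach is limited to morphine equivalents, the functional recovery index and, if treated as continuous, time to regular shoe gear.

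The textual conclusion rests on sentence order and on the separate binary rule, and needs no numerical assumption. The fall from 80% to about 55% rests entirely on assumed normal data, 40 per arm, an assumed difference and a median split that is not in the plan, so it should be cited only as hypothetical. The point is minor, but the text is wrong as it stands and is easily put right before analysis.

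**What to change.** In the continuous-data sentence, delete the reference to Fisher's exact test. State instead that, for continuous secondary outcomes, the two-sided p-value of the t-test or Wilcoxon rank sum test actually used decides significance at p ≤ 0.05. Report a 95% confidence interval from the matching analysis: for the difference in means with the t-test, and for the Hodges-Lehmann shift with the Wilcoxon test. Keep Fisher's exact test for binary data only.

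The cost is a change of one sentence. It needs no new data and no change to the sample size, the outcomes or the visit schedule.

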#### **Missing Data**

Given that the first outcome measure occurs within two days and the second outcome occurs in twelve weeks of study enrollment, we do not anticipate that missing data will be a large concern. Protocol deviations will be recorded and reported but the primary analysis will be an **intent-to-treat analysis**. For outcomes requiring a longer follow-up duration, any patients who are lost, move or expire will be counted as treatment failures. Patients will be generally healthy as this is a population undergoing elective bunionectomy surgery. In addition, information will be collected regarding patient contact information to help prevent loss of patients. Patients that miss a follow-up appointment will have a set mechanism in-place in order to contact the patients. All available contact information

including the patient's residential and work address, work, home and cellular phone number as well as contact information of the next of kin and closest friend will be obtained for each patient. Permission to contact these people as necessary will be obtained. The short follow-up period will also improve success in these measures. Finally, there is a built in 10% increase in patient sample size if the above safety measures still fail.

Although we do not anticipate significant missing data problems, any concerns will be dealt with sensitivity analyses to determine their impact.

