*h. Week Twelve and Subsequent Visits:* Weight bearing anteroposterior and lateral foot radiographs will be taken and the patient will be clinically assessed at week twelve  $\pm$ 1 week. If there is complete osseous union on radiographs, the patient will have completed the study. If there is incomplete osseous union on radiographs, the patient will continue to be followed by his/her surgeon. The timing and frequency of these subsequent visits will be determined by the patient's surgeon.

If there is incomplete osseous union after twelve weeks, the patient will be classified as a delayed union. If there is incomplete osseous union after six months, the patient will be classified as a nonunion.

**The post-operative care described here is considered standard of care for this procedure (except for the study drug, telephone call, study diary, and questionnaires) and not related to the study.**

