### **B. Statistical Considerations**

#### **a. Sample Size Justification:**

In performing the required sample size calculations, the authors assumed that potential cluster effects may be evident as a function of the individual surgeon. Because of this likelihood of cluster effects, we estimate the power of the study for change in post-operative pain that assumes an intra-class correlation (ICC) of at least 0.08 to inflate sample size estimates. This assumes 80% power to detect differences between groups with a 0.05 two-sided significance. Previous literature reports that in comparisons of opioid alone versus ketorolac with opioid the mean difference was observed to be 1.8 on the VAS (16). The widely accepted minimum clinically significant pain relief has been reported to be 1.3 (17). Detection of a 1.3 absolute difference in change in pain relief between groups requires 40 patients per group; detection of a 1.8 difference requires 20 patients per group consisting of eight and four (surgeons) respectively, assuming clusters of 10 subjects each. These calculations use an extremely high ICC which maximizes its accuracy. Because of the unknown ICC influence, a sensitivity analysis was performed assuming a non-contributory ICC of 0.08 which required a total sample size of 20 subjects per arm using the smallest clinically significant difference to detect.

Based on these calculations the largest sample required is 80 subjects. In order to preserve statistical power in the face of drop-outs and patient contact difficulties, the total sample size will be inflated by 10% such that the final projected sample size will be 88 subjects, or 44 per arm.

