The next consideration for study design is the sample size calculations for delayed and nonunion in each group. Because earlier calculations have already incorporated ICC assumptions, the previous approach is still considered appropriate. Again drawing from higher level studies, the difference to detect has been determined to be 20.5% between groups (38). Using the same criteria from the previous calculations, an 80% power to detect differences between groups with a 0.05 two-sided significance will require a total sample size of 76, or 38 subjects per arm. If the ICC were to be changed to 0.01 detection of a 20.5% difference requires 40 patients per group with five clusters of sixteen patients for the total of 80 subjects. Given the ICC assumptions of the VAS calculations the authors have already attempted to incorporate a highly conservative sample calculation and included a 10% inflation for drop-outs.

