The patient diaries with the VAS will be collected during the first post-operative visit (one week). Patients will be asked to bring all surgery related medications and bottles to this post-operative appointment. The research fellow will again obtain the patient's post-operative pain medication consumption (including timing and dosages) by counting pills and verbally confirm study protocol compliance (Please refer to the variables collected section for full details).

Whether a difference in delayed unions at twelve weeks exists between the two groups will also be assessed. Radiographic union for each patient will be assessed by both a blinded, board-certified radiologist and two blinded board-certified podiatric surgeons. Agreement between these three experts will be assessed with a kappa score and the mean result will be used for primary analysis. Delayed and non-union rates will be compared between the two groups. A previously documented scoring system found to have both high inter- and intra-observer reliability in a series of tibial fractures reduced surgically will be utilized for this assessment. This scoring system grades each fracture according to four characteristics: 1. Rating of fracture healing, 2. Callus morphology, 3. Number of cortices visible or obliterated. 4. Number of cortices bridged (41). The modification utilized for this study will be as follows:

- ❖ **Grade 1:** Homogenous bone structure with complete obliteration of fusion site
- ❖ **Grade 2:** Massive bone trabeculae crossing fusion site, 3-4 cortices are bridged with fusion site barely discernable
- ❖ **Grade 3:** Apparent bone trabeculae crossing fusion site, 2-3 cortices are bridged with fusion site discernable
- ❖ **Grade 4:** Trace bone trabeculae crossing fusion site, 1-2 cortices are bridged with distinct visible joint space

- ❖ **Grade 5:** No bone trabeculae crossing fusion site, 0 cortices are bridged with complete visible joint space

A delayed-union will be defined as a grade 4 or 5 in any patient over twelve weeks. A nonunion will be defined as a grade 4 or 5 in any patient over six months. Analysis will include logistic regression for these binary endpoints. Odds ratios and 95% confidence intervals will be calculated between groups (delayed and/or non-union: yes/no). A 2-sided p value of  $\leq 0.05$  will be considered statistically significant.

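### Counting lost patients as treatment failures records bone-healing harms without a radiograph; the rule's reach and its sensitivity analyses need to be specified

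*Combined protocol and SAP*

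**What the plan says.** The rule is in B3, Statistical Considerations, Missing Data: "For outcomes requiring a longer follow-up duration, any patients who are lost, move or expire will be counted as treatment failures". Treatment failure is not defined. Just before it, the section notes that "the first outcome measure occurs within two days and the second outcome occurs in twelve weeks of study enrollment", so *longer* could mean longer than two days, which takes in delayed union at week 12, or longer than twelve weeks, which leaves only six-month nonunion. The section closes by saying that "any concerns will be dealt with sensitivity analyses to determine their impact", without naming a method or scenario.

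The healing endpoint is defined under Data Analysis, Primary Outcome. Radiographic grade 4 or 5 is delayed union after twelve weeks and nonunion after six months. Groups are compared by logistic regression with odds ratios ("delayed and/or non-union: yes/no").

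Follow-up after week 12 is set in A.4, Week Twelve and Subsequent Visits: "If there is complete osseous union on radiographs, the patient will have completed the study". The others stay with their surgeon, and "The timing and frequency of these subsequent visits will be determined by" that surgeon.

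Three kinds of withdrawal are not named in the rule: after a serious adverse event that stops study drug (A.7), for pregnancy (section C) and by the surgeon's decision (B5). Both the Primary Outcome and Missing Data sections promise an intention-to-treat analysis.

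**The concern.** Treating lost patients as failures is usually cautious when failure means lack of benefit. Here failure means harm, and whether ketorolac delays bone healing is the trial's main safety question. Adding the same proportion of imputed events to both arms shrinks the contrast. Adding clearly more to one arm manufactures a contrast. Either way the answer depends partly on who was lost, and the imputed event does not meet the plan's own definition, which needs a grade.

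The plan allows for loss by adding patients ("in the face of drop-outs and patient contact difficulties, the total sample size will be inflated by 10" percent). That replaces lost information; it does not undo dilution from counting the lost as events. The patients withdrawn under A.7, section C or B5 have no stated healing outcome at all, and withdrawal after an adverse event could plausibly differ by arm.

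**Working it through.** **Inputs.** From the plan: 44 per arm; two-sided 0.05; a 10% allowance for drop-out; and, for the healing endpoint, "the difference to detect has been determined to be 20.5% between groups". The 88 reproduces as 80 × 1.10. The plan gives no control rate for this procedure and no loss forecast. I therefore assume control rates of 2% to 15%. The value 3.45% is the pilot's 1/29 nonunions, which came from ketorolac-treated patients having a different bunion procedure, so it is only a placeholder.

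**Formula if the rule reaches week 12.** With loss f in both arms and true rate p, the counted rate is f + (1 − f)p on 44 per arm. Observed films number 44(1 − f) per arm, or 40 at 10% loss.

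At f = 10%:
- control: 0.10 + 0.90 × 0.0345 = 13.1%
- ketorolac: 0.10 + 0.90 × 0.2395 = 31.6%
- the difference falls from 20.5 to 18.45 points
- the odds ratio falls from (0.2395/0.7605)/(0.0345/0.9655) = 8.8 to (0.3155/0.6845)/(0.131/0.869) = 3.1
- imputed share of control-arm events: 0.10 × 0.9655/0.131 = 74%

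**Power by exact binomial enumeration, rule v observed films (%).** Likelihood-ratio power from a one-covariate logistic model is within about 1 point of chi-square.

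| Control rate | Loss | Chi-square | Wald |
|---|---|---|---|
| 3.45% | 2% | 80 v 86 | 65 v 57 |
| 3.45% | 5% | 70 v 85 | 63 v 54 |
| 3.45% | 10% | 57 v 83 | 54 v 50 |
| 10% | 10% | 50 v 65 | 48 v 60 |
| 15% | 10% | 47 v 57 | 46 v 56 |

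The Wald column does not fall at the low control rate because tables with no events in one arm are non-significant under Wald, and imputed events remove such tables.

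**A worked trial, 4 lost per arm.** Observed 9/40 v 1/40 (odds ratio 11.3, 95% CI 1.4 to 94) becomes 9 + 4 = 13/44 v 1 + 4 = 5/44 (odds ratio 3.3, 1.05 to 10.2). After the rule, p is 0.032 by likelihood ratio, 0.041 by Wald and 0.062 by Fisher (0.014 before). Arm-specific bounds run from 9/44 v 5/44 (9.1 points, Fisher p = 0.38) to 13/44 v 1/44 (27.3 points, p = 0.0007). The rule's 18.2 points is one value inside that range. With 1 lost per arm, 9/43 v 1/43 (Fisher p = 0.015) becomes 10/44 v 2/44 (p = 0.026).

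**No drug effect, unequal loss, true rate 3.45%.** Rejection under the rule, Fisher (chi-square in brackets): loss 2% v 5%, 2% (9%); 8% v 12%, 4.5% (9%); 5% v 10%, 6% (12%); 5% v 15%, 18% (28%). On observed films Fisher is at most 1% and chi-square at most 2.7%. The likelihood-ratio test already rejects about 8% on observed films because events are few, so Fisher is the cleaner guide here.

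**If the rule covers six-month nonunion only.** A grade 4 or 5 at week 12 is already an event on the combined endpoint, so later loss of that patient changes only nonunion reported alone. Suppose true nonunion is 3.45% in both arms, delayed union is 10% v 30.5% (44 × 0.10 = 4.4 v 44 × 0.305 = 13.4 patients), and a share g of delayed unions is lost. Counted nonunion is 3.45% + g(d − 3.45%), where d is the delayed-union rate, so the false gap is 20.5g points:
- g = 10%: 4.1% v 6.2%, Fisher rejection 1%
- g = 25%: 5.1% v 10.2%, 6%
- g = 50%: 6.7% v 17.0%, 21%

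The combined endpoint is not wholly untouched. A.4 keeps patients with incomplete union in follow-up, but only grades 4 and 5 are events. A patient at grade 3 or better with incomplete union can still be followed after week 12, be lost, and become an event.

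**The case against.** The plan expects little missing data, sets out contact tracing, and treats the visits and films as standard of care. Counting the lost as failures keeps every randomised patient in the comparison. Observed-grade analysis leaves some out and assumes films are missing at random. The day-two pain outcome is not affected. If *longer* means beyond twelve weeks, the week-12 power figures do not apply. The nonunion figures also need loss rates that have no source in the plan.

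All of that stands, and it limits the size of the point. It does not remove it, because the rule as written still assigns a harm without a film and leaves its reach open.

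Two stronger readings are tempting. First, a reader might infer that near 10% loss the rule would turn a significant harm signal into a non-significant one. In the worked trial that happens only with Fisher. The plan specifies logistic regression for this endpoint, and there the result stays nominally significant. Second, a reader might take a large power loss as a general property of the planned analysis. The plan does not say which logistic test is used, and at control rates of about 3.5% or below the Wald test shows no loss. Nor is it right that the plan omits sensitivity analyses: it promises them but names none.

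**Conclusion.** The concern holds as a cheap improvement. On a yes/no harm endpoint the stated rule dilutes the odds ratio under equal loss and, under a large imbalance, can produce a false difference. The fall in the odds ratio does not depend on the choice of test. The power cost does: at 10% loss, likelihood-ratio and chi-square power drop by 26 points at a 3.45% control rate and by 15 at 10%, while Wald power drops about 10 to 12 points only at control rates of 10% to 15%. With about one loss per arm the conclusion is unchanged, and clear false-positive inflation by Fisher needs something like 5% v 15% loss. If the rule covers only six-month nonunion, the effect falls mainly on nonunion reported alone and is material only at high loss. All sizes rest on assumed control and loss rates; only the 10% allowance, the 20.5 points and the 44 per arm are the plan's.

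**What to change.** 1. State which outcomes the rule covers, in particular whether delayed union at week 12 is included.
2. Base the main delayed-union and nonunion comparison on observed panel grades by randomised arm. Keep lost-equals-failure as a named sensitivity analysis. Add an arm-specific best/worst-case or tipping-point analysis, because applying failure to both arms cannot bound the result.
3. Reconcile the withdrawals in A.7, section C (Pregnancy) and B5 with the intention-to-treat commitment, so that standard-of-care films of withdrawn patients stay in the analysis where consent continues. The drug-stopping and withdrawal rules themselves are not changed.

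The cost is protocol and SAP wording and two short analyses, with no extra visit, film or reader. The downside is that the main comparison omits randomised patients with no grade and assumes films are missing at random; the sensitivity analyses show how far the result depends on that.
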